#### 6.5.4. Concomitant medications and non-drug treatments

The following analyses will be based on the safety analysis set by treatment arm.

**Concomitant medications** are medications, other than study drugs, which started prior to first dose date of study treatment and continued during the on-treatment period as well as those started during the on-treatment period. **Prior medications** are medications, other than study drugs and pre-medications for study drug, which are started before the first dose of study treatment.

Prior and concomitant medications will be summarized from the 'General Concomitant Medications' eCRF page. Pre-medications for study drug will also be summarized separately from the 'Pre-Medication Treatment' eCRF page.

Summary of prior medications, summary of concomitant medications and summary of pre-medications will include the number and percentage of patients by Anatomical Therapeutic Chemical (ATC) Classification level 2 and preferred term. A patient will be counted only once within a given drug class and within a given drug name, even if he/she received the same medication at different times. If any prior or concomitant medication is classified into multiple ATC classes, the medication will be summarized separately under each of these ATC classes. The summary tables will be sorted on decreasing frequency of drug class and decreasing frequency of drug name in a given drug class. In case of equal frequency regarding drug class (respectively drug name), alphabetical order will be used. In case any specific medication does not have ATC classification level 2 coded term, it will be summarized under 'Unavailable ATC classification' category.

A listing of prior medications and a listing of concomitant medications will be created with the relevant information collected on the 'General Concomitant Medications' eCRF page. A listing of pre-medications will be created with the relevant information collected on the 'Pre-Medication Treatment' eCRF page.

All concurrent procedures, which were undertaken any time during the on-treatment period, will be listed according to the eCRF page 'General Non-drug Treatments'.

A listing of concurrent procedures will be created with the relevant information collected on the ‘General Non-drug Treatments’ eCRF page.

### 6.5.5. Subsequent anti-cancer therapies

The following analyses will be based on the FAS by treatment arm.

Anti-cancer treatment will be provided in a data listing with data retrieved from ‘Follow-up Cancer Therapy’, ‘Follow-up Radiation Therapy’, ‘Concomitant Surgery’, and ‘Follow-up Surgery’ eCRF pages.

Number and percentage of patients with any anti-cancer therapy after discontinuation will be tabulated overall and by type of therapy based on the data collected from the ‘Follow-up Cancer Therapy’, ‘Follow-up Radiation Therapy’ and ‘Follow-up Surgery’ eCRF pages.

## 6.6. Safety Summaries and Analyses

The Safety Analysis Set will be the primary population for safety evaluations. Summaries of AEs and other safety parameters will be based on the safety analysis set by treatment arm.

### 6.6.1. Adverse events

Treatment-emergent adverse events (TEAEs) are those events with onset dates occurring during the on-treatment period as defined in Section 3.5.1.

All analyses described will be based on TEAEs (started during the on-treatment period) if not otherwise specified. The AE listings will include all AEs (whether treatment-emergent or not). AEs with onset outside the on-treatment period will be flagged in the listings.

- **Related Adverse Events:** adverse events with relationship to study treatment (as recorded on the AE eCRF page, Relationship with study treatment = Related) reported by the investigator and those of unknown relationship (ie, no answer to the question ‘Relationship with study treatment’). Related AEs are those related to any study drug (ie, at least one of the study drugs).
- **Serious Adverse Events (SAE):** serious adverse events (as recorded on the AE eCRF page, Serious Adverse Event = Yes).
- **Adverse Events Leading to Dose Reduction:** adverse events leading to dose reduction of study treatment (as recorded on the AE eCRF page, Action taken with study treatment = Dose reduced).
- **Adverse Events Leading to Interruption of Study Treatment:** adverse events leading to interruption of study treatment (as recorded on the AE eCRF page, Action taken with study treatment = Drug interrupted). The eCRF does not allow for a clear separation between interruption of an infusion and delays of administration for a parenteral drug as both are recorded using the same term on the eCRF (“Drug interrupted”). IRRs will be excluded in the analysis of AEs leading to Drug Interruption in case they only led to an interruption of the infusion.

- **Adverse Events Leading to Permanent Treatment Discontinuation:** adverse events leading to permanent discontinuation of study treatment (as recorded on the AE eCRF page, Action taken with study treatment = Drug withdrawn).
- **Adverse Events Leading to Death:** adverse event leading to death (as recorded on the AE eCRF page, Outcome = Fatal, as well as AEs of Grade 5).
- **Immune-related Adverse Events (irAE):** irAEs (as identified according to the methodology outlined in Appendix 1 for a pre-specified search list of MedDRA PTs documented in the SRP and finalized for analysis of this study's data prior to DB lock)
- **Infusion-related Reactions (IRR):** IRRs (as identified according to the methodology outlined in Appendix 2 for a pre-specified search list of MedDRA PTs documented in the SRP and finalized for analysis of this study's data prior to DB lock).

Unless otherwise specified, AEs will be summarized by number and percentage of patients with the AE in the category of interest as described above, by treatment arm, primary SOC and PT in decreasing frequency based on the frequencies observed for Arm A.

Each patient will be counted only once within each SOC or PT. If a patient experiences more than one AE within a SOC or PT for the same summary period, only the AE with the strongest relationship or the worst severity, as appropriate, will be included in the summaries of relationship and severity.

#### 6.6.1.1. All adverse events

Adverse events will be summarized by worst severity (according to NCI-CTCAE version 4.03) per patient, using the latest version of MedDRA preferred term (PT) as event category and MedDRA primary system organ class (SOC) body term as Body System category.

In case a patient has events with missing and non-missing grades, the maximum of the non-missing grades will be displayed. No imputation of missing grades will be performed.

The following tables will be created:

- The overall summary of AEs table will include the frequency (number and percentage) of patients with each of the following by treatment arm:
  - TEAEs;
  - TEAEs, Grade  $\geq 3$ ;
  - Related TEAEs;
  - Related TEAEs, Grade  $\geq 3$ ;
  - TEAEs leading to dose reduction of avelumab;
  - TEAEs leading to dose reduction of cisplatin;
  - TEAEs leading to dose reduction of IMRT;
  - TEAEs leading to interruption of avelumab;

- TEAEs leading to interruption of cisplatin;
  - TEAEs leading to interruption of IMRT;
  - TEAEs leading to discontinuation of avelumab;
  - TEAEs leading to discontinuation of cisplatin;
  - TEAEs leading to discontinuation of IMRT;
  - TEAEs leading to discontinuation of any study drug (CRT Phase);
  - TEAEs leading to discontinuation of all study drugs (CRT Phase);
  - Related TEAEs leading to discontinuation of avelumab;
  - Related TEAEs leading to discontinuation of cisplatin;
  - Related TEAEs leading to discontinuation of IMRT;
  - Related TEAEs leading to discontinuation of any study drug (CRT Phase);
  - Related TEAEs leading to discontinuation of all study drugs (CRT Phase);
  - Serious TEAEs;
  - Related Serious TEAEs;
  - TEAEs leading to death;
  - Related TEAEs leading to death;
  - irAEs;
  - IRRs.
- TEAEs by SOC and PT and worst grade
  - Related TEAEs by SOC and PT and worst grade
  - TEAEs leading to death by SOC and PT
  - Related TEAEs leading to death by SOC and PT

In addition, the following tables will be created by treatment phase:

- Overall summary of AEs table will include the frequency (number and percentage) of patients with each of the following by treatment arm and treatment phase a :
  - TEAEs;
  - TEAEs, Grade  $\geq$  3;
  - TEAEs leading to discontinuation of avelumab;
  - Serious TEAEs;
  - irAEs;
  - IRRs.
- TEAEs by SOC and PT and worst grade.

- TEAEs leading to death by SOC and PT.

a AEs will be included in the summary for each treatment phase if the AE onset occurs anytime from first dose of study treatment in the treatment phase through minimum (first dose of study treatment in next treatment phase, end of on-treatment period).

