#### **5.4.2.2. Administration**

Cisplatin is highly emetogenic. After administering appropriate antiemetics (see [Section 5.5.2.1](#)), cisplatin will be infused over 60-120 minutes for the 100 mg/m^2 dose along with vigorous hydration per local standard of care. Please refer to the study Investigational Product (IP) manual for further details regarding cisplatin administration.

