**Figure 1. Study Design Schema**

- a. Patients with LA SCCHN (oral cavity, oropharynx, larynx, or hypopharynx) eligible for front-line treatment: HPV negative disease stage III, IVa, IVb; non-oropharyngeal HPV positive disease stage III, IVa, IVb; HPV positive oropharyngeal disease T4 OR N2c OR N3 (staging per TNM [tumor, node, metastases] guidelines for head and neck sites AJCC 7th Edition). (Note: entry criteria for patients with HPV-positive tumors are different than for HPV-negative tumors).
- b. Avelumab or placebo IV to be administered on Day 1 of the Lead-in Phase (1 week prior to the start of the CRT Phase), and on Days 8, 25, and 39 during the CRT Phase.
- c. SOC CRT = IMRT (70 Gy/35 fractions/7weeks; 1 fraction/day, 5 fractions/week) for 7 weeks + cisplatin (100 mg/m^2 Days 1, 22, 43) during the CRT Phase.
- d. Maintenance Phase to start after completion of the CRT Phase and continue for 12 months.
- e. Patients will continue treatment until confirmed disease progression as assessed by Investigator per modified RECIST v1.1.

AJCC = American Joint Committee on Cancer; CRT = chemoradiotherapy; HPV = human papillomavirus; IMRT = intensity-modulated radiation therapy; LA = locally advanced; Q2W = every 2 weeks; RECIST = Response Evaluation Criteria in Solid Tumors; SCCHN = squamous cell carcinoma of the head and neck; SOC = standard of care.

There will be 3 treatment phases in this study.

- **Lead-in Phase:** On Day 1 of the Lead-in Phase of the study, patients will receive a single dose of avelumab or matching placebo, administered 7 days prior to initiation of the CRT Phase;
- **CRT Phase:** Avelumab or matching placebo will be administered on Days 8, 25, and 39 in conjunction with SOC CRT starting on Day 1 of the CRT Phase;
- **Maintenance Phase:** Following completion of the CRT Phase, avelumab or matching placebo will be administered Q2W for 12 months during the Maintenance Phase.

The treatment schedule is described in Table 2.

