**Table 2. Chemoradiation and Avelumab/Placebo Treatment Schedule**

	Lead-in Phase (7 days) a	CRT Phase (63 days)								Maintenance Phase b
	-- Day --	----- Day -----								
	1	1	8	15	22	25	29	36	39	43
IMRT (70 Gy/35 fractions/7 weeks; 1 fraction per day, 5 fractions/week [Monday – Friday])		X→	X→	X→	X	→	X→	X→	→	X→
Cisplatin (100 mg/m^2 Q3W)		X			X					X
Avelumab (10 mg/kg) or placebo	X		X		X c			X		Q2W

- Lead-in Phase to start 7 days prior to initiation of CRT Phase.
- Maintenance Phase to start after completion of the CRT Phase (ie, 2 weeks following completion of CRT) and be 12 months in duration. CRT phase may be extended as required for patient recovery from CRT; however, it is hypothesized that patients will receive maximal benefit from beginning maintenance as close to the scheduled time as possible.
- Day 25 dose of avelumab/placebo during the CRT Phase may be administered between Day 24 and Day 29. Cisplatin should be administered on a Monday or Tuesday if feasible to maximize overlap with IMRT. CRT = Chemoradiotherapy; IMRT = intensity-modulated radiation therapy; Q2W = every 2 weeks; Q3W = every 3 weeks.

The investigator will assess antitumor activity based on radiological assessments and clinical evaluation of patients using modified RECIST v1.1 at baseline, 12 weeks after the completion of CRT (ie, 10 weeks following completion of the CRT Phase of the study), every 16 weeks thereafter for 48 months (208 weeks), and every 24 weeks thereafter until confirmed disease progression per modified RECIST v1.1 and regardless of discontinuation of study treatment or initiation of subsequent anti-cancer therapy.

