### **Start dates of study treatment within each treatment phase:**

- Lead-in Phase

The start date/time of study treatment is the first dose date/time of avelumab or matching placebo across the Lead-in Phase visits.

- CRT Phase

The start date/time of study treatment is the earliest dose date/time of avelumab or matching placebo, cisplatin or IMRT across the CRT Phase visits.

- Maintenance Phase

The start date/time of study treatment is the earliest dose date/time of avelumab or matching placebo across the Maintenance Phase visits.

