### 3.5. Safety Endpoints

#### 3.5.1. Adverse events

##### Treatment-Emergent Adverse Events

Treatment-emergent adverse events (TEAEs) are those events with onset dates occurring during the on-treatment period.

**On-treatment period** is defined as the time from the first dose of study treatment through minimum (30 days + last dose of study treatment, start day of new anti-cancer drug therapy – 1 day). The start day of new anti-cancer drug therapy after the first dose of study treatment is derived as outlined in Section 5.2.5.

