#### **6.5.3.2. Exposure to Cisplatin**

Cisplatin is to be administered only in the CRT Phase. Three doses of cisplatin (100 mg/m^2) are planned to be administered on Days 1, 22, and 43 of the CRT Phase.

**Intended duration of cisplatin treatment** in CRT Phase (weeks) = 63/7 = 9 weeks

**Duration of exposure to cisplatin** in the CRT Phase (weeks) =

$$(\text{last dose date of cisplatin} - \text{first dose date of cisplatin} + 21) / 7$$

**Cumulative cisplatin dose** (mg/m^2) is the sum of the actual doses of cisplatin received in the CRT Phase.

**Actual Dose Intensity (DI)** for cisplatin in the CRT Phase =

$$[\text{cumulative dose (mg/m}^2\text{)}] / [\text{intended duration of cisplatin treatment (weeks)} / 9] \text{ (mg/m}^2\text{/9-weeks)}$$

**Relative Dose Intensity (RDI)** for cisplatin in the CRT Phase is calculated as follows:

- Intended DI (mg/m^2/9-weeks) = 300 (mg/m^2/9-weeks)
- RDI (%) = 100 × [actual DI] / [intended DI] = 100 × actual DI / 300.

The summary of treatment exposure and compliance for cisplatin will include the following information:

- Duration of exposure to cisplatin (weeks);

- Total number of doses a received;
- Cumulative dose (mg/m^2);
- Actual DI (mg/m^2/9-weeks);
- RDI (%).

a Per protocol, cisplatin dose can be split over a period of 2 to 4 consecutive days. Therefore, if cisplatin is given consecutively over 2-4 days, this will be viewed as a split dose. Split doses will be summed up and categorized as a single dose.

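### The by-phase AE windows share their boundary day, so AEs starting on CRT Day 1 also enter the Lead-in tables and those starting on the first Maintenance day also enter the CRT tables

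*SAP*

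**What the plan says.** SAP 6.6.1.1, footnote a, sets the window for the by-phase AE tables. An AE is included if "AE onset occurs anytime from first dose of study treatment in the treatment phase", and the window runs "through minimum (first dose of study treatment in next treatment phase, end of on-treatment period".

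SAP 3.4.1 defines where each phase starts. For CRT: "The start date/time of study treatment is the earliest dose date/time of avelumab or matching placebo, cisplatin or IMRT across the CRT Phase visits". SAP Table 2 labels the first column "Lead-in Phase (7 days" and gives the CRT Phase 63 days. SAP 2.2 describes the Lead-in: "patients will receive a single dose of avelumab or matching placebo, administered 7 days prior to initiation of the CRT Phase". SAP 6.5.3.2 places the first cisplatin dose on the opening day of CRT: "Three doses of cisplatin (100 mg/m 2 ) are planned to be administered on Days 1, 22, and 43 of the CRT Phase".

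Other SAP rules separate adjoining periods. The on-treatment period in SAP 3.5.1 (repeated in 5.2.7) ends at the smaller of two terms, "30 days + last dose of study treatment, start day of new anti-cancer drug therapy", with one day subtracted from the second. A Maintenance cycle in SAP 6.5.3.1 ends the day before the next one starts. The by-phase laboratory rule in SAP 6.6.5.1 uses date and time for both the test and the dose. Footnote a neither subtracts a day nor mentions time.

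**The concern.** If both ends of a window are included and the next window opens on the day the previous one closes, that day belongs to two phases. The first shared day matters most. It is the day cisplatin and radiation start, and Protocol 5.4.2.2 states that "Cisplatin is highly emetogenic". Nausea or vomiting that begins a few hours after the first cisplatin infusion would be tabulated as a Lead-in event.

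The Lead-in shows what avelumab does compared with placebo before CRT is added. By-phase safety summaries were introduced in SAP version 3, so these tables are meant to be read. CRT toxicity in the Lead-in columns of both arms would raise both rates and blur the comparison. At the other boundary, reactions to the first Maintenance infusion would also be listed under CRT.

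**Working it through.** The plan states no figure to reproduce. The check applies footnote a to the planned schedule, counting Lead-in Day 1 as study day 1.

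**Inputs**
- Lead-in length 7 days and CRT length 63 days (SAP Table 2).
- First day of CRT: 1 + 7 = day 8.
- First planned Maintenance dose: 8 + 63 = day 71.
- AE onset is handled by date. The imputation rules in SAP 5.3.2.2 fill in dates only. The IRR definitions in SAP Appendix 2 use onset date plus a before/during/after marker relative to the infusion. No clock time for AE onset is described.

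**Window length = last day − first day + 1**

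| Phase | As written | Length | Closing one day earlier | Length |
|---|---|---|---|---|
| Lead-in | days 1–8 | 8 − 1 + 1 = 8 | days 1–7 | 7 − 1 + 1 = 7 |
| CRT | days 8–71 | 71 − 8 + 1 = 64 | days 8–70 | 70 − 8 + 1 = 63 |
| Maintenance | from day 71 | – | from day 71 | – |

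**Phases into which an onset day falls**

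| Onset day | As written | Closing one day earlier |
|---|---|---|
| 7 | Lead-in | Lead-in |
| 8 | Lead-in and CRT | CRT |
| 9 | CRT | CRT |
| 70 | CRT | CRT |
| 71 | CRT and Maintenance | Maintenance |
| 72 | Maintenance | Maintenance |

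As written, 1 of the 8 Lead-in window days (1/8 = 12.5%) is a cisplatin and radiation day. With one day subtracted, each onset day has exactly one phase and the lengths match the planned 7 and 63. If CRT is extended, the second shared day moves to the actual first Maintenance dose, but it is still shared.

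**Does another rule resolve the tie?** SAP 6.6.1 counts a patient once per SOC or PT and resolves multiple events within one summary period. It does not choose between phases. SAP 6.6.1.4, 6.6.2, 6.6.3 and 6.6.4 also call for by-phase summaries but state no window of their own.

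**Which Lead-in outputs are exposed?** In SAP 6.6.1.1: TEAEs, Grade 3 or higher TEAEs, serious TEAEs, the IRR row that is not limited to one drug, and the SOC/PT tables.

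**The case against.** The best counter-argument is that footnote a refers to a dose, not a dosing day, and that SAP 3.4.1 defines phase starts by date and time specifically to support by-phase safety summaries. On that reading the overlap shrinks to one instant, and an AE after the first CRT dose belongs to CRT alone. This would settle the matter if AE onset had a clock time. The SAP describes none, and it mentions date and time only in the laboratory rule. The before/during/after marker could help place boundary-day events, but footnote a does not use it. At the least, two programmers could produce different tables.

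Several limits on the consequences do stand:
- Maintenance is also avelumab or placebo alone. A reader might infer that the Lead-in is the only such period. It is the only one before CRT.
- A reader might infer that all by-phase IRR and irAE tables are contaminated at the start of CRT. The detailed by-phase IRR tables in SAP 6.6.4 are limited to IRRs associated with avelumab or leading to its discontinuation, and no avelumab is planned on CRT Day 1. The irAE definition in SAP Appendix 1 requires a listed term, specific treatment and an etiology check, so ordinary same-day CRT toxicity would largely be filtered out.
- Both arms receive the same CRT, so the spill-over is not inherently differential.
- SAP 3.5.1 describes safety analyses as generally exploratory, and all AEs are listed.

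**Conclusion.** The point holds. Read by date, footnote a assigns CRT Day 1 to both Lead-in and CRT, and the first Maintenance day to both CRT and Maintenance. This rests on AE onset being available only as a date, which is how the SAP treats it.

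The size is unknown. A reader might assume that 10% to 40% of patients have an AE starting on the first cisplatin day and arrive at 64 to 256 patients (640 × 0.10 and 640 × 0.40). The documents give no such rate. That calculation also treats every randomized patient as receiving cisplatin, although Protocol 1.2.2 reports 72 cisplatin starters among 78 randomized at the first E-DMC data cutoff. It attributes every Day 1 event to CRT, and it ignores patients who already have a Lead-in event and so add nothing to an any-TEAE row.

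A reader might also infer double counting in the main safety results. The documents do not support this: an event appears once in each of two adjacent phase tables, and the overall AE tables are unaffected. Avelumab-associated IRR tables are not materially affected at the Lead-in/CRT boundary, although at CRT/Maintenance such reactions would appear in both phases. Efficacy, alpha and power are untouched. This is a limited defect in descriptive tables that should be corrected before they are programmed.

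**What to change.** - In SAP 6.6.1.1, footnote a, end each phase window at the earlier of (i) the first dose date of the following phase minus 1 day and (ii) the end of the on-treatment period.
- Assign an AE with onset on the following phase's first dosing day to that later phase, unless the recorded before/during/after timing shows that it began before dosing.
- State that this rule governs all by-phase AE, SAE, irAE, IRR and death summaries, including those in SAP 6.6.1.4 and 6.6.2 to 6.6.4.
- In SAP 6.6.5.1, keep date and time for laboratory tests but end the window strictly before the first dose date/time of the next phase. Its closing point is currently also inclusive.

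The cost is a few words in the SAP and a minor programming change. No additional data are needed.

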#### **6.6.1.2. Adverse events leading to dose reduction**

The frequency (number and percentage) of patients with each of the following will be presented for TEAEs leading to dose reduction of each study drug by treatment arm:

- TEAEs leading to dose reduction of avelumab by SOC and PT;
- TEAEs leading to dose reduction of cisplatin by SOC and PT;
- TEAEs leading to dose reduction of IMRT by SOC and PT.

The listing of all AEs leading to dose reduction will also be provided with the relevant information.

